**Progression-free survival (PFS), by cohort/sub-cohort:** PFS is defined as the time from the date of first dose of INC280 to the date of first radiologically documented disease progression per RECIST 1.1 or death due to any cause. PFS events documented after the initiation of new anti-neoplastic therapy (i.e. RECIST 1.1 documented disease progression or death) will be considered for the primary analysis provided tumor assessments continue after initiation of the new cancer therapy. Clinical deterioration will not be considered as a qualifying event for progression. PFS will be censored at the last adequate tumor assessment if one of the following occurs: absence of event; the event occurred after two or more missing tumor assessments. PFS will be described in tabular and graphical format, by cohort/sub-cohort, using Kaplan-Meier methods, including estimated median (in months) with 95% CI, 25th and 75th percentiles and Kaplan-Meier estimated probabilities with corresponding 95% CIs at several time points. Censoring reasons will also be summarized.

Additional analysis of all secondary efficacy objectives in pre-treated patients with a cMET GCN of  $\geq 10$  may be carried out combining the patients with a cMET GCN of  $\geq 10$  from Sub-

cohort 1a and Cohort 6 to further evaluate the precision of the efficacy estimates. Similar analysis will be carried out for pre-treated patients with cMET mutations regardless of cMET GCN combining the patients from Cohort 4 and Cohort 6. Cohort 7 may also be combined with Sub-cohort 5b.

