### **End dates**

The end dates which are used to calculate ‘time to event’ variables are defined as follows:

- Date of death (during treatment as recorded on the treatment completion page or during follow-up as recorded on the study evaluation completion page or the survival follow-up page).
- Date of progression is the first assessment date at which the overall lesion response was recorded as progressive disease.
- Date of last adequate tumor assessment is the date the last tumor assessment with overall lesion response of CR, PR or SD which was made before an event or a censoring reason occurred. In this case the last tumor evaluation date at that assessment is used. If no post-baseline assessments are available (before an event or a censoring reason occurred) the date of randomization/start of treatment is used.
- Date of next scheduled assessment is the date of the last adequate tumor assessment plus the protocol specified time interval for assessments. This date may be used if back-dating is considered when the event occurred beyond the acceptable time window for the next tumor assessment as per protocol (see [Section 14.1.26](#)).

**Example** (if protocol defined schedule of assessments is 3 months): tumor assessments at baseline - 3 months - 6 months - missing - missing - PD. Date of next scheduled assessment would then correspond to 9 months.

- Date of discontinuation is the date of the end of treatment visit.
- Date of last contact is defined as the last date the patient was known to be alive. This corresponds to the latest date for either the visit date, lab sample date or tumor assessment date. If available, the last known date patient alive from the survival follow-up page is used. If no survival follow-up is available, the date of discontinuation is used as last contact date.
- Date of secondary anti-cancer therapy is defined as the start date of any additional (secondary) antineoplastic therapy or surgery.

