2.8 Analysis of secondary variables

2.8.1 Efficacy

All secondary endpoint analyses will be performed based on the FAS, unless otherwise specified. Efficacy will also be presented combining the MET mutant cohorts per line of treatment as defined in [Section 2.2](#).

No adjustment for multiple testing will be made.

Key secondary efficacy endpoints

The key secondary objective is to evaluate duration of response (DOR) as assessed by BIRC, by cohort.

Among patients with a confirmed response (PR or CR), DOR is defined as the time from first documented response (PR or CR) to the date of first documented PD or death due to any cause. If a patient has not had an event, DOR is censored at the date of last adequate tumor assessment.

The censoring and event date options to be considered for the main analysis are presented in [Table 2-1](#).

Table 2-1 Outcome and event dates for DOR and PFS analyses

Situation	Date	Outcome
A No baseline assessment	Date of first dose of study drug ^a	Censored
B Progression at or before next scheduled Assessment	Date of progression	Progressed
C1 Progression or death after exactly one missing assessment	Date of progression (or death)	Progressed
C2 Progression or death after two or more missing assessments	Date of last adequate assessment	Censored
D No progression	Date of last adequate assessment	Censored
E Treatment discontinuation due to 'Disease progression' without documented progression, i.e. clinical progression based on investigator claim	N/A	Information ignored. Outcome derived based on radiology data only.
F New anticancer therapy given	Ignore the new anticancer therapy and follow situations above	As per above situations
G Deaths due to reason other than deterioration of 'Study indication'	Date of death	Progressed

^a The rare exception to this is if the patient dies no later than the time of the second scheduled assessment as defined in the protocol in which case this is a PFS event at the date of death

DOR will be described in tabular and graphical format using Kaplan-Meier methods. The Kaplan-Meier estimate of the distribution function will be constructed. Kaplan-Meier curves

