If a patient has not progressed or is not known to have died at the date of analysis cut-off, PFS will be censored at the date of the last adequate tumor evaluation before the cut-off date. PFS events documented after the initiation of new anti-neoplastic therapy (i.e. RECIST 1.1 documented disease progression or death) will be considered for the primary analysis provided tumor assessments continue after initiation of the new cancer therapy. Clinical deterioration will not be considered as a qualifying event for progression. Refer to [Table 2-1](#) for censoring and event date options and outcomes for PFS.

In particular, PFS will be censored at the last adequate tumor assessment if one of the following occurs: absence of event; the event occurred after two or more missing tumor assessments (see [Section 4.6.1](#)). See also [Section 4.6.1](#) describing the special case of a missing baseline tumor assessment.

Patients with no BIRC data will be considered censored at the start date of study drug.

PFS will be described in tabular and graphical format using Kaplan-Meier methods as described for DOR by cohort, including estimated median (in months) with 95% CI, 25th and 75th percentiles and Kaplan-Meier estimated probabilities with corresponding 95% CIs at several

time points. Censoring reasons will also be summarized by cohort. These analyses will be performed separately based on BIRC assessment and based on investigator assessment.

In addition, PFS table will be repeated on the PPS.

Overall survival (OS)

OS is defined as the time from the start date of study drug to the date of death due to any cause. If the patient is alive at the date of the analysis cut-off or lost to follow-up, then OS will be censored at the last contact date prior to data cutoff date (see [Section 4.3](#) for further details on derivation of last contact date).

OS will be described in tabular and graphical format using Kaplan-Meier methods as described for DOR by cohort, including estimated median (in months) with 95% CI, 25th and 75th percentiles and Kaplan-Meier estimated probabilities with corresponding 95% CIs at several time points. Censoring reasons will also be summarized by cohort.

OS from initial diagnosis to the date of death due to any cause will also be analyzed. Date of censoring is the same as defined for OS analysis.

Duration of Follow-up

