As detailed in Section 14 (Appendix II) of the CINC280A2201 protocol, the PFS censoring and event date options depend on the presence and the number of missing tumor assessments. *For example, an event occurring after two or more missing assessments is censored in the analysis of PFS at the last adequate tumor assessment before the event date.*

An exact rule to determine whether there is none, one or two missing assessments is therefore needed. This rule will be based on the distance between the last adequate tumor assessment date and the event date.

If the distance is larger than threshold D_1 or D_2 then the analysis will assume one or two missing assessments, respectively. The threshold D_1 will be defined as the protocol specified interval between the tumor assessments plus the protocol allowed window around the assessments. Similarly, the threshold D_2 is defined as two times the protocol specified interval between the tumor assessments plus the protocol allowed window around the assessments. In this study, the protocol defined schedule of tumor assessment is every 6 weeks and each assessment is expected to be performed at the scheduled time point plus or minus 1 week, i.e. the window is 2 weeks, then any distance larger than $D_1 = 6+2 = 8$ weeks means one missing assessment and any distance larger than $D_2 = (2*6) + 2 = 14$ weeks means two missing assessments.

The same definition of D_2 will be used to determine the PFS censoring reason.

Possible censoring reasons for PFS are:

- 1: Ongoing without event
- 2: Lost to follow-up
- 3: Withdraw consent
- 4: Adequate assessment no longer available

5: New cancer therapy added

6: Event after ≥ 2 missing tumor assessments

PFS censoring reason is then derived by the following sequence of rules.

- If patient is considered to have a PFS event then PFS censoring reason is set to missing.
- Else if patient has had no baseline assessment then PFS censoring reason = 4.
- Else if patient has a PFS event after two or more missing assessments [If (PFS Event date \leq Censoring date and (PFS Event date - Date of last adequate tumor assessment (LATA) \geq D2)] then PFS censoring reason =6:
- Else if patient has no PFS event, and patient is censored at a date after two or more missing assessments ((Censoring date - Date of LATA) \geq D2) then PFS censoring reason = 4
- Else if censoring date equals the start date of further anti-neoplastic therapy then PFS censoring reason = 5

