- Else if censoring date equals date of discontinuation due to consent withdrawal then PFS censoring reason = 3
- Else if censoring date equals date of discontinuation due to loss to follow-up then PFS censoring reason = 2
- Else if the censoring date equal the analysis cut-off date and the time between LATA and the cut-off is greater than D2 days then PFS censoring reason = 4
- Else if the censoring date equal the analysis cut-off date and the time between LATA and the cut-off is less than or equal to D2 days then PFS censoring reason = 1

Where censoring date = minimum(analysis cut-off date, start date of further anti-neoplastic therapy, date of discontinuation due to consent withdrawal, date of discontinuation due to loss to follow-up).

Non-measurable disease at baseline

As specified in Section 14 (Appendix II) of the CINC280A2201 protocol, the RECIST 1.1 criteria imply that only patients with measurable disease at baseline should be included in the study. If a patient without measurable disease is enrolled, the intent-to-treat (ITT) principle requires including these patients in the analyses. Hence, analyses will be based on FAS including patients with either measurable or non-measurable disease. Therefore, a rule needs to be specified on how to handle these cases.

As specified in Table 3-1 of Section 14 (Appendix II) of the CINC280A2201 protocol, overall lesion response can be derived for patients without measurable disease at baseline as follows ([Table 4-3](#)).

Table 4-3**Overall lesion response at each assessment: patients with non-target disease only**

Non-target lesions	New Lesions	Overall lesion response
CR	No	CR
Non-CR/Non-PD ¹	No	Non-CR/non-PD
UNK	No	UNK
PD	Yes or No	PD
Any	Yes	PD

¹ In general, the **non-CR/non-PD response** for these patients is considered equivalent to an SD response in endpoint determination.

Missing baseline tumor assessment

As specified in Section 14 (Appendix II) of the protocol, since the timing of PD cannot be determined for patients with missing baseline tumor assessment, these patients are censored in the PFS analysis at the start date of treatment. This rule, however, only applies to the ‘PD component’ of the PFS or DOR assessment.

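### SAP 4.6.1 can report patients as censored for new anticancer therapy in a PFS analysis that does not censor for it

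*SAP*

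**What the plan says.** **How the main analysis treats new therapy.** SAP Table 2-1, which governs DOR and PFS, says for situation F: "Ignore the new anticancer therapy and follow situations above". The PFS text in SAP 2.8.1 and in protocol 10.5.2 says that events after new therapy "will be considered for the primary analysis provided tumor assessments continue after initiation of the new cancer therapy". Protocol 10.5.2 names two grounds for censoring, namely no event, and an event preceded by at least two missed scans. Its sentence opens with "PFS will be censored at the last adequate tumor assessment if one of the following occurs: absence of event; the event occurred after two or". New therapy is not one of the two grounds.

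**How the censoring reason is derived.** SAP 4.6.1 lists six reasons and applies rules in sequence. The first is "If patient is considered to have a PFS event then PFS censoring reason is set to missing". A later one is "Else if censoring date equals the start date of further anti-neoplastic therapy then PFS censoring reason = 5". The date used is defined at the end: "Where censoring date = minimum(analysis cut-off date, start date of further anti-neoplastic therapy, date of discontinuation due to consent withdrawal", with loss to follow-up as the last term. Reason 6 (event after two or more missing assessments) also uses this date, because the event must fall on or before it.

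**Where PFS time is censored.** SAP 2.8.1 censors PFS at the last adequate tumor evaluation before the cut-off. Its follow-up paragraph repeats that the PFS censoring date is the last adequate assessment.

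**The appendix.** Protocol 14.1.25 defines the last adequate assessment as one "which was made before an event or a censoring reason occurred". Table 14-5 makes censoring at new therapy a default only where the protocol or analysis plan does not specify otherwise. Protocol 14.1.39 lists new therapy among the possible censoring reasons.

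**The concern.** Two parts of the SAP describe different analyses. Table 2-1 and 2.8.1 follow patients through a change of therapy. The reason algorithm in 4.6.1 reads as if follow-up stopped there.

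The situation is built into the design. Under protocol 4.1.4 and 7.1.5.2, patients who stop INC280 without BIRC-confirmed progression go on being scanned, and their new therapies are recorded. Protocol 7.2.1.5 allows a change of therapy on medical need when BIRC does not confirm progression, with imaging continuing.

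Readers use the censoring-reason summary to judge whether censoring is informative. As written, it would show patients as removed at new therapy when they were not. It would also hide some events that were censored because scans had been missed.

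**Working it through.** The plan states no figure to reproduce, so this is a check of one set of rules against another.

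**Inputs.** From SAP 4.6.1: D2 = (2 × 6) + 2 = 14 weeks = 98 days, and the rules in this order:
1. PFS event: reason missing.
2. No baseline assessment: reason 4.
3. Event on or before the censoring date, and event − last adequate assessment (LATA) ≥ D2: reason 6.
4. No event, and censoring date − LATA ≥ D2: reason 4.
5. Censoring date = new-therapy start: reason 5.
6. Censoring date = consent withdrawal: reason 3; = loss to follow-up: reason 2.
7. Censoring date = cut-off: reason 4 if more than D2 after LATA, otherwise reason 1.

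**Hypothetical patients.** All have cut-off on day 300 and new therapy on day 100. As written, the minimum is day 100 for each of them. In the corrected run, new-therapy start is left out of the minimum.

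| Patient | As written | New therapy left out |
|---|---|---|
| (a) No event, LATA day 294 | 100 − 294 = −194, so rule 4 fails; rule 5 gives **reason 5** | Date 300; 300 − 294 = 6 < 98; **reason 1** |
| (b) PD day 210 after two or more missed scans, LATA day 84 | 210 > 100, so rule 3 fails; **reason 5** | 210 ≤ 300 and 210 − 84 = 126 ≥ 98; **reason 6** |
| (c) No event, consent withdrawn day 200, LATA day 168 | 100 − 168 = −68, so rule 4 fails; **reason 5** | Date 200; 200 − 168 = 32 < 98; **reason 3** |
| (d) PD day 210, scans continuing, LATA day 168 | 210 − 168 = 42 < 98; an event under Table 2-1; reason missing | Same |

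Patients (a) to (c) are mislabelled; (d) is not. In (b) the PFS time is the same under either label, because Table 2-1 situation C2 censors at day 84 regardless.

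The negative differences in (a) and (c) are informative. Rule 4 is meaningful only if the last adequate assessment precedes the censoring date. That suggests the algorithm was written for an analysis that stops at new therapy. The generic list in protocol 14.1.39 is a likely source.

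**What would have to happen for PFS times to change.** A programmer would have to treat the minimum date as the censoring reason in protocol 14.1.25 and discard later scans. With scans every 42 days, patient (a) would then be censored at day 84 instead of day 294, and patient (d) would lose an event at day 210. The SAP does not instruct this.

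**The case against.** The strongest reply is that this is a labelling slip in a descriptive table. The minimum date exists only inside the reason derivation. Events are settled first, and PFS time runs to the last adequate assessment before the cut-off. A program that truncated at new therapy would have to disregard Table 2-1 and the PFS text of SAP 2.8.1. All of this stands, and it rules out three stronger readings that a reader might infer:

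- **That the PFS estimates are wrong.** The documents do not support this. Times change only if the appendix wording is misapplied as described above.
- **That every patient who starts new therapy before BIRC-confirmed progression gets a wrong reason.** Patients with a counted event get no reason. Those without a baseline assessment get reason 4. Those with no event whose last adequate assessment is at least 98 days before new therapy also get reason 4. An earlier withdrawal or loss date takes precedence over new therapy.
- **That DOR is affected too.** The 4.6.1 reason algorithm is written for PFS. DOR shares Table 2-1, which is the rule that ignores new therapy.

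It is also fair to say that the protocol does not simply ignore new therapy. Its rule depends on assessments continuing, and its appendix names new therapy as a possible reason. But that appendix list is generic, and protocol 10.5.2 sets the study's own grounds for censoring without including new therapy. SAP Section 3 declares no change to the protocol's analyses. The objection reduces the size of the point but does not remove the contradiction.

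**Conclusion.** Wrong as written; minor, and limited to the PFS censoring-reason summary. The patients affected are those who are censored, whose new-therapy start is the earliest of the four dates, and who reach the reason-5 rule. They would be reported as censored for new therapy when the analysis did nothing of the kind.

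The documents do not say how many there are. The worked patients show the mechanism, not a frequency. The conclusion assumes that 4.6.1 is programmed literally and that Table 2-1 is the intended main analysis. The primary endpoint is unaffected, because SAP 2.7.1 has its own rule excluding assessments after new therapy from best overall response.

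**What to change.** For the main PFS analysis, remove new-therapy start from the minimum in SAP 4.6.1 and drop reason 5. Alternatively, keep both only for a separately labelled sensitivity analysis that censors at new therapy. In either case, add a sentence that in the main analysis the last adequate assessment is not truncated at new therapy, so that the wording of protocol 14.1.25 cannot be read the other way.

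One side effect should be accepted knowingly. A patient whose scans stop at the switch will fall to the remaining rules, and will appear as ongoing without event if the cut-off is within 14 weeks of the last scan. If the frequency of switching is of interest, tabulate it separately.

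The cost is a few lines of SAP text and a small program change. No new data are needed.

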4.6.2 Sources for overall lesion response

The tumor endpoints derivation is based on the sequence of overall lesion responses at each assessment/time point. However, the overall lesion response at a given assessment/time point will be provided from different sources as illustrated in [Table 4-5](#).

Table 4-5 Sources for overall lesion response

Source 1	BIRC (Blinded Independent review committee) reported overall lesion response
Source 2	Investigator (local radiology) reported overall lesion response

In this study, Source 1 will be used for the primary endpoint derivation and other secondary endpoint calculations based on BIRC assessment (ORR, DOR, DCR, TTR and PFS). Source 2 will be used to calculate ORR, DOR, DCR, TTR and PFS by Investigator assessment.

4.6.3 Kaplan-Meier estimates

To analyze time to event variables (DOR, TTR, OS and PFS) an estimate of the survival function will be constructed using ***Kaplan-Meier (product-limit) method*** as implemented in PROC LIFETEST with METHOD=KM option (see example below). The median time to event and estimated event rates at different time points will be estimated, along with associated 95% two-sided CIs derived based on the complementary log-log transformation. This will be conducted via the SAS procedure LIFETEST. The TIME statement will include a variable with survival times (*survtime* in the example below) and a (right) censoring variable (*censor* in the example below) with a value of 1, representing censoring:

```
PROC LIFETEST data = dataset
  METHOD = KM
  CONFTYPE=LOGLOG;
  TIME survtime*censor(1);
  RUN;
/* survtime represents variable containing event/censor times;
   censor represents censoring variable (1 = censored, 0 = event); */
```

Kaplan-Meier survival and failure function estimates from this procedure will be used to construct the Kaplan-Meier figures.

Median survival will be obtained along with 2-sided 95% CIs calculated from PROC LIFETEST output using the method of [Brookmeyer & Crowley, 1982](#).

Kaplan-Meier estimates with 2-sided 95% CIs at specific time points will be summarized. The time points can be expressed in weeks or in months depending on the time-to-event variable. The CIs will be constructed using Greenwood's formula [\[Collet, 1994, p.23\]](#) for the standard error of the Kaplan-Meier estimate.

The Kaplan-Meier graphs will be constructed using SAS software.

4.6.4 Confidence interval and p-value for response rate

ORR will be summarized in terms of percentage rates with 95% CIs. An exact binomial confidence interval (implemented using SAS procedure FREQ with EXACT statement for one-way tables) will be calculated ([Clopper & Pearson, 1934](#)).

SAS procedure FREQ will be used to estimate the proportion of responders (binary outcome = 1 or “Yes”), along with the associated 95% ($=100 \times (1 - \text{two-sided alpha level})$) two-sided Pearson-Clopper CI and exact one-sided p-value for the hypothesis test of the *null proportion* (0.25). These estimates are obtained as follows:

```
proc freq data = dataset;
  table binary event /
    binomial(
      p = null proportion
      level = "Yes")
    alpha = two-sided alpha level;
  exact binomial;
```

When there are no responders, SAS does not produce a CI by default. To obtain a CI in this situation, PROC FREQ is used as specified above except changing **level**="No". From the results of this modified procedure, the values in percent of the LCL and UCL of a 0% response rate are calculated as follows:

$$\text{LCL}_{\text{LEVEL}=\text{"Yes"}\ (\%)} = 100\% - \text{UCL}_{\text{LEVEL}=\text{"No"}\ (\%)}$$

$$\text{UCL}_{\text{LEVEL}=\text{"Yes"}\ (\%)} = 100\% - \text{LCL}_{\text{LEVEL}=\text{"No"}\ (\%)}$$

